# ON DEMOND SILDOSIN 4MG VS DAPOXITINE 60MG IN TREATMENT OF PRIMARY PREMATURE EJACULATION

Date 1-3-2024

Introduction

Premature ejaculation (PE) is a common sexual problem encountered by men in day-to-day clinical practice. It affects about 20-30% of men in the sexually active age group. PE is a commonly used term, but it is more appropriately called early ejaculation or rapid ejaculation (Raveendran and Agarwal, 2021).

PE means ejaculation occurs within one minute during the sexuality with sex partner after inserting into the vagina, and this symptom lasts for at least 6 months. PE is defined by The American Urology Association as "ejaculation occurring sooner than desired causing distress to one or both partners" (Gillman and Gillman, 2019).

The etiology of PE is complex, and its pathogenesis is still unclear. It's believed that this disease is mostly related to psychological factors. The persistent unhealthy psychological factors may aggravate potential abnormal organic factors, which lead to the occurrence of premature ejaculation (*Coskuner and Ozkan, 2022*).

While PE is a common sexual dysfunction affecting all age groups, it is more prominent in older age groups and more commonly associated with other medical conditions like diabetes. Primary PE can be triggered by psychological impulses like conditioning, upbringing, or traumatic sexual experience. Secondary PE can be triggered by diabetes, hypertension, hyperthyroidism, alcoholism, or use of recreational drugs (*Raveendran and Agarwal*, 2021).

According to the time when the symptom of PE occurs, this disease could be divided into two types which are named preliminary premature ejaculation and acquired premature ejaculation (*Pereira-Lourenço et al.*, 2019).

PE causes psychological stress and loss of self-esteem, resulting in significant adverse effects on the quality of life, of both the patient and the partner. So, present therapeutic schedule mainly includes psychological

therapy, behavioral therapy, drug therapy and Chinese medicine. These therapies could be used alone or in combination, and relevant literature has reported certain clinical effects.

However, there are still many problems such as large side effects, high recurrence rate, and long-term efficacy uncertainty, which need to concentrate on (Abbas et al., 2023).

Thus, pharmacotherapy should in theory be the treatment of choice for patients with lifelong PE (Waldinger MD, et al .,2020).

Dapoxetine is a selective serotonin reuptake inhibitor, is the first oral pharmacological agent indicated for the treatment of men aged 18-64 years with premature ejaculation. (N Engl J Med. 2019).

Dapoxetine is the only effective and safe available on-label oral treatment for PE, and its use can result in better quality of life for the patient and their sexual partner. (N Engl J Med. 2019).

Oral dapoxetine 60 mg (administered as needed) was effective in the treatment of men with premature ejaculation, inducing significantly greater improvements. (N Engl J Med. 2019).

Silodosin is a selective alpha-1a adrenergic antagonist used in the therapy of benign prostatic hypertrophy. Silodosin is associated with a low rate of serum aminotransferase elevations and to rare instances of clinically apparent acute liver injury. (N Engl J Med. 2019).

Silodosin inhibits alpha adrenergic receptors present on smooth muscle in the bladder neck and prostate (alpha-1a adrenergic receptors)(N Engl J Med. 2019).

Compared with other  $\alpha 1$ -adrenoceptor antagonists, silodosin appeared to suppress ejaculation in a relatively higher percent of trial participants.

This suppression of ejaculation by silodosin suggested its potential for treating premature ejaculation and it seemed to be more effective for preventing PE than other alpha blockers. (Sato Y, Otani T, et al. 2017).

.

## Aim of the Work

The aim of this study is to assess efficacy and tolerability of Silodosin 4mg vs Dapoxitine 60mg in treatment of primary premature ejaculation.

## **Patients and Methods**

A prospective study will be carried out on 50 patients with premature ejaculation who attending outpatient clinic, urology department, Benha university hospitals over a period of 6 months starting from approval of the institutional ethical committee.

An informed written consent will be obtained from the patients. Every patient will receive an explanation of the purpose of the study and will have a secret code number.

Research results will only be used for scientific purposes. Any unexpected risks appearing during research will be clarified to the participants and to the ethical committee on time.

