## Study design:

Patients who meet the previous criteria will be enrolled in the study.

We randomly assigned 80 outpatients with PPE to two groups , group A (sildosin 4mg) 40 patients and group B (dapoxatine 60mg) 40 patients .

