#### 2. Clinical Examination:

A thorough clinical examination of the patients will be conducted to evaluate their general health and assess any physical signs and symptoms related to premature ejaculation or other conditions.

Group A (sildosin 4 mg): intake 2h before intercourse (on demand) at least 6 times intercourse /month for 2 months.

Group B (dapoxatine 60mg): the same like sildosin.

**Follow up** patients will be evaluated by PEP (premature ejaculatory profile) & IELT. (intravaginal latency time) 2 months after start of treatment.

Intravaginal ejaculatory latency time (IELT): normal duration 2.5- 5 minutes. (Waldinger MD, et al .2005).

scores of the Premature Ejaculation Profile (PEP): to evaluate the reliability and validity of the Premature Ejaculation Profile (PEP), The

PEP contains four measures: perceived control over ejaculation, personal distress related to ejaculation, satisfaction with sexual intercourse, and interpersonal difficulty related to ejaculation, each assessed on five-point response scales. (Patrick DL, et al.,2009).

Any side effects of drugs will be recognized and recorded.

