## **Ethical considerations:**

- 1. An approval from the Research Ethics Committee of faculty of medicine will be obtained.
- 2. An informed written consent from all patients or first-degree relatives before participation will be obtained; it will include data about aim of the work, study design, site, time, subject and methods, confidentiality.
- 3. Official permission will be obtained from the Dean of Faculty of Medicine and the administrators of University Hospitals to conduct this study.

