#### Statistical analysis

We will use IBM's Statistical Package for the Social Sciences (2017, Released) to edit, code, and tabulate the data we gathered. IBM Corp., Armonk, New York, USA: IBM SPSS Statistics for Windows, Version 25.0. To ensure that the data was distributed normally, the Shapiro-Wilk test was employed. Each parameter's data type informed the presentation and analysis of the corresponding data. Nominal data were expressed as mean ± SD. For categorical data, percentages and frequencies were employed. The statistical significance of a difference between two study groups for parametric variables was assessed using an independent samples t-test, and for non-parametric variables, the Mann Whitney Test (U test) was employed. We looked examined the correlation between the two qualitative variables using the Chi-Square test. At a 95% confidence interval, a p-value is deemed significant if it is less than 0.05.

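### The protocol gives two incompatible sample sizes: 50 patients under Patients and Methods, 80 randomised (40 per group) under Study design

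*Combined protocol and SAP*

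**What the plan says.** The protocol states the size of the study twice.

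- **Patients and Methods:** "A prospective study will be carried out on 50 patients with premature ejaculation". The sentence is in the future tense and gives no group sizes.
- **Study design:** "We randomly assigned 80 outpatients with PPE to two groups", namely "group A (sildosin 4mg) 40 patients and group B (dapoxatine 60mg) 40 patients". This is in the past tense, but the sentence just before it is in the future: "Patients who meet the previous criteria will be enrolled in the study".

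No section gives a sample-size calculation, a power, a standard deviation, a target difference, a dropout rate or a designated primary endpoint. On testing, the Statistical analysis section says only that "a p-value is deemed significant if it is less than 0.05" and names the independent-samples t-test or, alternatively, the Mann-Whitney test.

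**The concern.** Both statements are current, complete and legible, they describe the same study, and they cannot both be the number of patients in it. The number studied sets the precision of both comparisons in the Aim of the Work, efficacy and tolerability.

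With two totals on record, a reader cannot tell what a finished trial should look like. A trial of 80 could be on plan or 30 patients over it. A trial stopped at 50 could be complete or 30 short. That leaves room for an undisclosed choice of when to stop, and the protocol exists partly to rule that out.

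**Working it through.** **1. Is each statement consistent with itself?** Study design: 40 + 40 = 80, so yes. Patients and Methods gives only the total of 50.

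**2. Size of the gap.** 80 − 50 = 30 patients. 80/50 = 1.60, so the larger figure is 60% above the smaller. 1 − 50/80 = 0.375, so the smaller is 37.5% below the larger.

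**3. Can any reading link the two figures?**

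- *Screened versus randomised:* no. Those randomised are a subset of those studied, yet the randomised figure is the larger.
- *50 per group:* no. Study design gives 40 per group.
- *50 evaluable out of 80 randomised:* Patients and Methods describes no evaluable set. Inflating 50 for dropout by 50/(1 − d) gives 56 at d = 10%, 63 at 20% and 72 at 30%. It reaches 80 only at d = 37.5%, and no dropout rate is stated.
- *Plan versus count reached:* verb tense does not decide it. Study design moves from future to past between adjacent sentences. Ethical considerations puts approval in the future ("An approval from the Research Ethics Committee of faculty of medicine will be obtained"). Statistical analysis describes work still to be done in the past tense ("for non-parametric variables, the Mann Whitney Test (U test) was employed"). So 80 may be a plan written in the past tense, or a count already reached with 50 as a superseded target.

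**4. Can either total be derived?** No. The inputs to a power formula are absent, so there is no planned calculation to reproduce.

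**5. What the choice is worth.** The 5% level, the t-test and the equal split of 80 come from the protocol. My assumptions are a two-sided test and the same equal split applied to 50, giving 25 per group. Results are in SD units because no SD is given.

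| Quantity | 25 per group | 40 per group |
|---|---|---|
| Detectable difference, 80% power (noncentral t) | 0.809 SD | 0.634 SD |
| Detectable difference, 90% power (noncentral t) | 0.936 SD | 0.734 SD |
| 95% CI half-width for a mean difference | 0.569 SD | 0.445 SD |
| Upper 95% limit for a side effect with no cases in an arm | 13.7% | 8.8% |

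- *Half-width:* t(0.975; 2n − 2) × √(2/n). For n = 25, 2.011 × 0.283 = 0.569. For n = 40, 1.991 × 0.224 = 0.445. The ratio is 0.569/0.445 = 1.28.
- *No cases observed:* upper limit of the two-sided exact (Clopper-Pearson) interval, 1 − 0.025^(1/n). For n = 25 this is 0.137 and for n = 40 it is 0.088.
- *Cross-check:* the normal approximation (1.960 + 0.842) × √(2/n) gives 0.79 and 0.63 SD at 80% power. This is slightly optimistic at 25 per group, as expected.
- *Mann-Whitney:* if the data were normal, dividing the t-test values by √(3/π) gives about 0.83 and 0.65 SD at 80% power.

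**The case against.** The contradiction itself has no good defence. The objections are to what is built on it.

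- **No section says 25 per group.** True. That figure comes from halving 50 in line with the equal allocation under Study design. The documented conflict is between two totals, and only one of them has group sizes. The 25 is an assumption and is labelled as such.
- **How the conflict arose is unknown.** Also true. No recruitment record is visible, and the past tense is weak evidence that anyone has been randomised. An overrun of 30 patients is a possibility, not a finding, so the correction has to cover each case.
- **The SD-unit figures are rough.** They are. The Premature Ejaculation Profile measures are five-point scales, the Mann-Whitney figure assumes normal data when the plan keeps that test for non-parametric variables, and the no-cases limit bounds a single arm rather than a difference between arms. The figures show only that the choice of total matters. The contradiction does not depend on them.
- **Settling on 80 may not be free.** Patients and Methods allows 6 months. If that period must also contain the follow-up at "2 months after start of treatment" (an assumption), 4 months remain for recruitment: 50/4 = 12.5 patients a month, or 80/4 = 20. This is a fair point about feasibility, but it does not reconcile the totals.
- **Asking for a precision statement goes beyond the inconsistency.** It does, and the core correction stands without it.

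**Conclusion.** The concern holds. The protocol commits to 50 patients in one section and to 80 in another, a difference of 30, and nothing in the document explains it or shows which is intended. This rests on the text alone and needs no assumption.

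Under the stated assumptions, the two totals differ in detectable difference by 0.81 versus 0.63 SD at 80% power, and the confidence interval is 28% wider at the smaller size. The sample size is a basic commitment of the protocol, so this must be corrected and is more than a typing slip. The documents do not show which number is right; only the sponsor can say.

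**What to change.** First establish whether 80 is the planned number or the number already randomised, and which total was put to the ethics committee. Then give one total, with matching group sizes, under both Patients and Methods and Study design.

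- **If 80 is the plan:** correct Patients and Methods to 80 and put the Study design sentence in the future tense.
- **If 50 is the plan and nobody has been randomised:** change Study design to 25 per group, assuming equal allocation is kept.
- **If 80 were already randomised against a plan of 50:** leave 80 under Study design and record the original target, the date of the change and the reason.
- **If recruitment is under way but incomplete:** state the number randomised so far and the target, and record any change of target in the same way.

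Two additions are useful but secondary. Beside the chosen total, name the outcome it refers to and give the detectable difference or CI half-width it delivers, with the assumptions, described as the precision obtained and not as a justification of the size. Also state that there will be a single analysis, after the last patient completes the 2-month follow-up.

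The core correction is to wording and recruits nobody extra. If 50 is the true figure, the precision to be reported is less favourable. If 80 were randomised against 50, the departure must be disclosed. If 80 is confirmed as a target still to be reached, the 6-month period should be checked against it.

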#### **Inclusion Criteria:**

- Age > 18 years old.
- Patients with primary premature ejaculation (PPE) according to (IELT < 1 min)

- Sexually active.
- Heterosexual.
- The course of suffering from PE is  $\geq 6$  months.

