#### **Exclusion criteria:**

- History of diabetes and other diseases.
- Uncontrolled hypertension (HTN) (systolic ≥ 140 mmHg or diastolic ≥ 90 mmHg).
- Patients having anatomic abnormalities of the penis or genital region
- Patients' refusal.
- Patients with erectile dysfunction.
- Patient with chronic prostatitis.
- Patient with psychologically disorder.
- Patient on anti-psychiatric drugs.

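### The age criterion has no upper limit, although the protocol gives 18-64 years as the indicated range for dapoxetine, and enrolling men above that range is not explained

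*Combined protocol and SAP*

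**What the plan says.** The Inclusion Criteria contain one statement on age: "Age > 18 years old". It sets a lower bound only. The Exclusion criteria list eight items, none of which refers to age. The broadest is "History of diabetes and other diseases".

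The Introduction says of dapoxetine that it "is the first oral pharmacological agent indicated for the treatment of men aged 18-64 years with premature ejaculation".

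Study design then makes the listed criteria the whole test for entry: "Patients who meet the previous criteria will be enrolled in the study". It continues with "We randomly assigned 80 outpatients with PPE to two groups", the comparator arm being "group B (dapoxatine 60mg) 40 patients".

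**The concern.** The protocol states an age range for the comparator's indication and then sets an eligibility rule that runs past the top of it. A clinician applying the criteria as written would have no ground for turning away a sexually active, otherwise healthy man of 65 or over with primary premature ejaculation, and randomisation could place him on dapoxetine 60 mg.

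Two things are at stake. The first is exposure: a participant could take the comparator at an age outside the range the document quotes, without the document acknowledging or justifying it. The second is interpretation. The Aim of the Work includes tolerability, and side effects are to be recorded in both groups. Events and responses in men above the quoted range would be pooled with the rest, because the Statistical analysis section plans simple two-group tests with no breakdown by age.

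**Working it through.** The protocol gives no figure to reproduce on this point. The check is a comparison of sections, with one line of arithmetic for allocation.

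**Inputs**

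| Item | Where | Content |
|---|---|---|
| Age criterion | Inclusion Criteria | Over 18, no upper bound |
| Age-based exclusion | Exclusion criteria | None |
| Age range given for the dapoxetine indication | Introduction | 18 to 64 years |
| Rule for entry | Study design | All who meet the criteria are enrolled |
| Allocation | Study design | 40 to silodosin 4 mg, 40 to dapoxetine 60 mg |

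**Step 1. Upper end.** Eligible ages are everything above 18. The quoted indication stops at 64. Men of 65 or over are therefore eligible and outside the quoted range.

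**Step 2. Lower end.** A criterion of over 18 admits nobody younger than 18. No one below the quoted range can enter, so the only mismatch that allows exposure outside it is at the top.

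**Step 3. Indirect limits.** The exclusions for diabetes and other diseases, uncontrolled hypertension, erectile dysfunction and chronic prostatitis, together with the requirement to be sexually active, may remove many older men. None of them works as an age ceiling. A man over 64 with none of these conditions still qualifies.

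**Step 4. Chance of receiving the comparator.** With the stated arm sizes, 40/80 = 0.5. If *k* men of 65 or over were randomised, about *k*/2 would be expected on dapoxetine 60 mg.

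**Step 5. Size of *k*.** The documents give no age distribution for the clinic or for the expected sample, so *k* cannot be calculated. Zero is possible.

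**Step 6. Any justification elsewhere.** The remaining sections (Patients and Methods, Clinical Examination, Ethical considerations, Statistical analysis) neither set an upper age nor explain enrolling men above 64.

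**The case against.** The strongest reply is that this is a small gap between a background sentence and an eligibility line. The 18-64 range describes an indication and is not a dosing or entry rule. The Introduction's statement that 60 mg was effective carries no age range. Silodosin is itself introduced as a drug for benign prostatic hypertrophy, so use within an indication is not the principle on which the trial is built. The health exclusions may leave few older men or none.

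Most of this stands, and it keeps the point minor. It does not remove the mismatch: the background sentence is the only place where the protocol says for whom the comparator is indicated, and eligibility departs from it without comment.

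A reader might infer more than the documents support, in four ways:

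- **That older candidates are likely.** The Introduction says of premature ejaculation that "it is more prominent in older age groups". That sentence concerns the condition in general and goes on to link it with illnesses such as diabetes, which this trial excludes. It is not evidence that healthy older men with primary disease will come forward.
- **That a definite number of men is affected.** Assuming 5-10% of 80 men are 65 or over gives 4-8 men, half of whom (2-4) would be on dapoxetine. With the 50 patients given under Patients and Methods, the same shares give 2.5-5 men and about 1-3 on dapoxetine. Nothing in the documents supports those shares, and a share of zero gives zero.
- **That the comparison is biased.** Random allocation would be expected to spread older men over both arms. No bias between arms follows from the wording.
- **That the lower bound also conflicts in a way that matters.** Read literally, it leaves out men aged exactly 18, which is narrower than the quoted range and exposes nobody outside it.

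**Conclusion.** The concern holds as an unexplained inconsistency at the upper end of the age range. As written, the criteria allow a man of 65 or over to be enrolled and, with a chance of one half, allocated to dapoxetine 60 mg outside the range that the Introduction quotes.

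Confidence is high on the textual mismatch, which rests on the wording alone. The practical effect is unknown: it depends on how many such men attend the clinic and pass the health exclusions, and the documents are silent on both. The conflict between 50 and 80 patients would change any count but not the conclusion. Severity is minor. It is worth correcting because tolerability is a stated aim and the correction is cheap.

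**What to change.** The investigator should reconcile the age criterion under Inclusion Criteria with the age range in the Introduction and apply the same criterion to both arms. Alternatively, the Inclusion Criteria should state the basis for enrolling men outside that range. Which course to take, and any limit chosen, is for the investigator to decide.

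Enrolment status is unclear, because the protocol mixes tenses and Study design describes randomisation in the past tense. If enrolment has begun, the sponsor should report by arm how many randomised men fall outside the quoted range, including a statement of none if that is the case.

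The cost is an edit to one criterion, or a short count if recruitment is under way. The possible downside is the loss of a few older candidates if the reconciliation narrows eligibility.

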#### **Exclusion criteria:**

- History of diabetes and other diseases.
- Uncontrolled hypertension (HTN) (systolic ≥ 140 mmHg or diastolic ≥ 90 mmHg).
- Patients having anatomic abnormalities of the penis or genital region
- Patients' refusal.
- Patients with erectile dysfunction.
- Patient with chronic prostatitis.
- Patient with psychologically disorder.
- Patient on anti-psychiatric drugs.

## Study design:

Patients who meet the previous criteria will be enrolled in the study.

We randomly assigned 80 outpatients with PPE to two groups , group A (sildosin 4mg) 40 patients and group B (dapoxatine 60mg) 40 patients .

#### **Methods:**

All patients meeting the above-mentioned criteria will be subjected to the following:

